Interaction of Melatonin and MTNR1B Genotype on Glucose Control - Study 1

NCT02642640

October 21, 2025

Study Protocol

Using a randomized, double-blind, placebo-controlled, cross-over design, we aim to determine the effects of 5 mg melatonin oral administration and its interaction with *MTNR1B* (encodes the high-affinity melatonin receptor 1B) genotypes on disposition index (DI), first-phase insulin release, insulin sensitivity, and glucose tolerance, using a high-frequency intravenous glucose tolerance test (IVGTT) performed in the afternoon. Both carriers of the *MTNR1B* risk SNP and non-carriers will be randomized to the order of conditions (melatonin/placebo) in a crossover design. The Internal Drug Services will follow a randomization scheme in which participants will be block-randomized (block size equals 2) into two treatment orders (melatonin/placebo or placebo/melatonin). Men and women will be randomized equally between the melatonin and placebo groups. Participants undergo one 5-day in-laboratory stay, during which participants maintain their habitual sleep/wake cycle as they have been doing for the 2-3 weeks prior to each admission. Following each admission and after a baseline day and night, participants receive 5 mg of melatonin or placebo during Wake Period (WP) 2, ~1h before the glucose infusion of IVGTT (ensuring peak levels at the start and high levels throughout the 3-h IVGTT). After two washout days and nights, on WP4, participants receive the opposite treatment to the one received on WP2. IVGTT's begin ~1h after melatonin/placebo administrations, and a mixed meal test begin ~1h after IVGTT ends. This approach allows us to assess an unresolved question which is whether melatonin and its interaction with the *MTNR1B* risk variant have a more profound impact on peripheral insulin sensitivity or, by contrast, on pancreatic insulin secretion. Investigational Drug Services (IDS) block-randomize participants (block size 2) into two treatment orders (melatonin/placebo or placebo/melatonin). In addition to the research participants, all personnel who have contact with the participants or with the endpoint assessment are blinded (all investigators, recruitment personnel, technicians, nurses, and physicians).

Statistical methods

We apply mixed model analysis on outcomes deduced from FSIGT, with melatonin/placebo as fixed factor, and individual as random factor (DI, insulin sensitivity, beta-cell function). To test the interaction effect with *MTNR1B* genotype, we use the same model, but include genotype (carriers vs. non-carriers) as a second fixed factor. Although genotype groups be matched for sex, age, and BMI, we test whether any of these factors are significant covariates. We also test for any order effects. Outcome variables exhibiting non-normality will be transformed as appropriate.

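### Treatment order is drawn in fixed blocks of 2 written into the protocol, with no stratification by genotype or sex described; stratified lists with varying, withheld block sizes would be a cheap improvement

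*Combined protocol and SAP*

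**What the plan says.** All the randomisation text is in the Study Protocol section. The block size is given twice: "participants will be block-randomized (block size equals 2) into two treatment orders" and, later, "Investigational Drug Services (IDS) block-randomize participants (block size 2) into two treatment orders". Nothing is said about varying the size or restricting who sees it. Two statements touch on subgroups. On genotype: "Both carriers of the *MTNR1B* risk SNP and non-carriers will be randomized to the order of conditions (melatonin/placebo) in a crossover design". On sex: "Men and women will be randomized equally between the melatonin and placebo groups". Neither names a stratum, a separate list or a minimisation procedure. The design is a full crossover, since on WP4 "participants receive the opposite treatment to the one received on WP2". On blinding, besides the participants, "all personnel who have contact with the participants or with the endpoint assessment are blinded", and the list of roles includes investigators and recruitment personnel.

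The Statistical methods section fits melatonin/placebo as a fixed factor and individual as a random factor, and adds genotype as a second fixed factor for the interaction. It says "Although genotype groups be matched for sex, age, and BMI, we test whether any of these factors are significant covariates". It also says that order effects will be tested, without giving the form of the test or what follows from it.

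**The concern.** There are three linked points.

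1. **Predictability.** In a fixed block of 2 the second order is always the opposite of the first. The protocol itself states this rule, so it gives no protection once one order in a pair is known.
2. **The sex sentence.** Everyone receives both treatments, so there are no melatonin and placebo groups between which to spread men and women. Only the order of treatments can be balanced, and the text does not say how that is done within sex.
3. **Balance within genotype.** The interaction with genotype is a stated aim. Matching the genotype groups on sex, age and BMI makes the groups alike, but does not balance treatment order within either group. If order differs between carriers and non-carriers, any WP2-to-WP4 change (from repeating the test within one stay, for example) enters the interaction estimate, because the model as described names no period term.

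**Working it through.** **Inputs from the documents:** block size 2, fixed; two orders; 1:1 allocation, implied by the block size; two periods; no period term named in the model. **Inputs not in the documents, so assumed:** number per genotype (10, 20, 30), total N (20 to 60), 50% women, genotype and sex unrelated to position on the list, and one pooled list. The plan states no figure on this point, so there is none to reproduce.

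**Step 1: determined orders.** For a block of size 2b, the expected share of assignments fully fixed by earlier ones in the block is 1/(b+1).
- Block 2: 1/2 = 50%
- Block 4: 1/3 = 33%
- Block 6: 1/4 = 25%

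Someone who knew all earlier orders and the position in the block would guess correctly 75.0%, 70.8% and 68.3% of the time, against 50% by chance (exact enumeration).

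**Step 2: order within genotype under one pooled list.** With n per genotype and complete blocks of 2, exactly n of the 2n participants are melatonin-first. The number X of carriers who are melatonin-first is then hypergeometric (2n, n, n). The difference in melatonin-first share between genotypes is (2X − n)/n, with SD 1/√(2n − 1).

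| n per genotype (assumed) | SD of difference | P(difference ≥ 20 points either way) |
|---|---|---|
| 10 | 1/√19 = 0.23 | 66% |
| 20 | 1/√39 = 0.16 | 34% |
| 30 | 1/√59 = 0.13 | 20% |

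At n = 20, simple randomisation gives an SD of 0.158, so pooled blocks of 2 do nothing for balance within genotype.

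**Step 3: effect on the interaction.** Let t be the melatonin effect, d the period effect (second minus first) and p the melatonin-first share in a genotype group. A melatonin-first participant contributes t − d to the melatonin-minus-placebo difference; a placebo-first participant contributes t + d. The group mean is p(t − d) + (1 − p)(t + d) = t + d(1 − 2p). The contrast between genotypes is therefore off by 2 × d × (difference in p). At 20 points this is 2 × 0.2 × d = 0.4d. At n = 20 the SD of this error is 2 × 0.16 × d = 0.32d. The documents give no value for d.

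**Step 4: is it bias?** Under a pooled list the expected difference in p is zero, so the expected error is zero. Simulating the interaction test without a period term at n = 20, with d equal to 0, 1 or 2 SD of the within-person difference, gives a type I error of about 5% in each case.

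**Step 5: order within sex under one pooled list (50% women).** The number of women differs between the two orders by 2 or more in 51%, 58%, 63% and 70% of simulated trials at N = 20, 30, 40 and 60, and by 4 or more in 12%, 20%, 27% and 36%. With separate lists by sex in blocks of 2, the difference never exceeds 1.

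**The case against.** A reader might infer that half the orders are open to the study team. The documents do not support that. The drug service runs the scheme, contact and endpoint staff are blinded, and no unblinding route is described. Deduction requires first learning or inferring an earlier order in the same list and knowing the position in the block. Nothing says which staff work from this text, although a protocol is not normally withheld from investigators.

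A reader might also infer that the promised sex balance fails. That is not shown either. Lists by sex or genotype are neither stated nor excluded, and blocks of 2 within sex would hold order to within one person. What stands is that the mechanism is not described and one pooled list would not guarantee balance.

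A third inference, that order imbalance biases the interaction, goes too far: Step 4 shows chance error with the type I error preserved.

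Three further objections carry weight. Blocks of 2 give the tightest balance of order, so the choice has a real benefit, and larger blocks give some of it up. Each participant receives both treatments, so foreknowledge of order cannot steer different people to melatonin and placebo; and knowing the WP2 treatment reveals WP4 at any block size. Finally, the plan does test for order effects. That helps only in part: the text does not say that period or order stays in the model, nor what is done with the result.

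**Conclusion.** The point holds as a low-severity improvement to the design. The fixed block size, its appearance in the protocol, the ill-fitting sex sentence and the absence of any described stratification are all on the page. The 50% figure follows from the block size alone, but matters only if an order becomes known. The imbalance figures (66%, 34% and 20% at 10, 20 and 30 per genotype) rest on an assumed sample size and an assumed pooled list, and fall as the sample grows. The consequence is loss of precision and of conditional balance in the melatonin x genotype estimate, in proportion to a period effect of unknown size. The main melatonin contrast is within-participant, and the pooled blocks of 2 already balance order overall.

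**What to change.** If randomisation is still open:
- Have the drug service prepare separate order lists for each genotype-by-sex stratum, with block sizes varying at random among small values (for example 2 and 4) and known only to the drug service.
- Keep the block sizes out of documents that blinded staff see.
- Replace the sex sentence with: *Treatment order will be balanced within genotype and sex.*

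If randomisation is complete:
- State whether separate lists by genotype or sex were used and how the sequence was concealed.
- Report treatment order by genotype and sex.
- Include period as a fixed effect in the mixed model, with a period x genotype check, in place of an unspecified test for order effects.

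The cost is a new list and a few sentences of text in the first case, and one table and one or two model terms in the second. The downside of varying blocks is slightly looser balance: one or two participants per stratum if its last block is incomplete (a block of 4 stopped halfway can leave a difference of 2, against at most 1 for a block of 2).

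### Does the stated washout contradict the wake-period schedule, and is there one admission or several?

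*Combined protocol and SAP*

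**What the plan says.** All of the schedule is in the Study Protocol section of the combined protocol and SAP.

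- **Number of stays:** "Participants undergo one 5-day in-laboratory stay".
- **Lead-in:** participants keep their habitual sleep/wake cycle, "as they have been doing for the 2-3 weeks prior to each admission".
- **First treatment:** "Following each admission and after a baseline day and night, participants receive 5 mg of melatonin or placebo during Wake Period (WP) 2".
- **Second treatment:** "After two washout days and nights, on WP4, participants receive the opposite treatment to the one received on WP2".
- **Time of day:** the endpoints are measured "using a high-frequency intravenous glucose tolerance test (IVGTT) performed in the afternoon", and "IVGTT's begin ~1h after melatonin/placebo administrations". The IVGTT lasts 3 h, and a mixed meal test starts about 1 h after it ends.

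The section gives no washout in hours. On the analysis side, the Statistical methods section names treatment as a fixed factor, individual as a random factor, and genotype as a second fixed factor for the interaction. It adds only: "We also test for any order effects".

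**The concern.** Two statements look as if they clash with the rest of the section.

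The first is the washout. The text uses one baseline day and night to get from the start of the stay to WP2, so its unit appears to be one wake period plus the night that follows. Applied after WP2 and its night, two such units are WP3 and WP4, and the second treatment would fall on WP5. The text says WP4.

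The second is the number of admissions. A single stay is stated, but the lead-in and the first dose are described for each admission, which suggests more than one.

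If either were a true conflict it could matter. A two-period crossover relies on the separation between treatments to keep the first drug, IVGTT and meal from affecting the second period. Whether both periods fall in one stay also bears on what a comparison of the two orders means.

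**Working it through.** **Inputs**, all from the Study Protocol section: baseline before WP2; first treatment on WP2; second treatment on WP4; dosing about 1 h before an afternoon IVGTT on both days, so at about the same clock time; a 3-h IVGTT; meal test about 1 h after it ends.

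**Sequence.** Wake periods and nights alternate: WP1, night 1, WP2, night 2, WP3, night 3, WP4, night 4, WP5.

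**Formula.** For doses on WP *a* and WP *b* at the same clock time:

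- complete wake periods between = *b* − *a* − 1
- nights between = *b* − *a*
- hours from dose to dose ≈ 24 × (*b* − *a*)

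| Second dose on | Complete wake periods between | Nights between | Hours from dose to dose |
|---|---|---|---|
| WP4 (named in the text) | 4 − 2 − 1 = 1 (WP3) | 4 − 2 = 2 | 24 × 2 = 48 |
| WP5 (inferred from a whole-day count) | 5 − 2 − 1 = 2 (WP3, WP4) | 5 − 2 = 3 | 24 × 3 = 72 |

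**Can the stated washout be reproduced?** It depends on what is counted.

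1. Complete wake periods: no. The gap holds one, and the text says two.
2. Nights: yes. The gap holds two.
3. Elapsed 24-h cycles from the first dose: yes, 48 / 24 = 2. The rest of WP2 with its night is one cycle in this count, and WP3 with its night is most of the next, up to the WP4 dose.

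The WP5 count in turn gives two complete days but three nights. Neither schedule therefore yields exactly two complete days and two nights, and the phrase is approximate on either.

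**Does the length of stay settle it?** No. If WP1 is taken as day 1 (an assumption), both WP4 and WP5 fall within five days.

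**Admissions, side by side.** One sentence states a single stay. The next describes the first treatment on WP2, and a later one places the opposite treatment on WP4, using the same numbering and referring back to WP2. No second stay, interval between stays or second baseline is described. The references to each admission make sense if they mean each participant's admission.

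**Does the analysis change?** The two order groups are melatonin then placebo, and placebo then melatonin. They are the same groups whether the second dose falls on WP4 or WP5. The model's factors (treatment, individual, genotype) and the order test use the same data under either count.

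**The case for a change.** The strongest case for acting is that the 48-h reading counts the first treatment's own test session as washout. The meal test starts about 1 + 3 + 1 = 5 h after the dose, and the protocol intends high melatonin levels through the IVGTT. From the start of the first meal test to the second dose is about 48 − 5 = 43 h, less than two full days. That reading also counts days differently from the baseline sentence. The analysis offers little support against carry-over, since no period term is named and the order test is not described further. The remedy would be only a few words.

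Part of this stands. WP2 is not a clean washout day, and the phrase does not match a count of complete days. An interval in hours and an explicit number of admissions would read better.

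The rest does not carry the point further:

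- A reader is not left without a schedule. Both treatment days are named, and WP5 arises only from extending the baseline count. The document also does not say when on WP1 participants are admitted, so the baseline day need not be a complete one.
- The carry-over argument needs 24 h more or less to matter. The documents give no elimination data and no information on how long an IVGTT or meal affects later tests, so they cannot show that 48 h is too short or that 72 h is needed.
- A missing period term would be a separate question about the model. It does not depend on how the washout is labelled.

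**Conclusion.** No change to the plan follows. The wording is loose in two places: the gap between treatments holds one complete wake period and two nights (about 48 h from dose to dose), and a single stay sits beside two references to each admission. Both are clerical. The most that turns on the washout phrase is 24 h (72 − 48), and that only if whole days are counted and the named wake period is set aside. Reconciling the passages is an editorial matter for the sponsor. It would not alter the order groups, the model or the order test.

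This rests on three assumptions: doses are given at about the same clock time on both days, as the afternoon IVGTT implies; the WP2 and WP4 numbering belongs to one stay, as the sequence reads; and the treatment days are those the text names. It is not a finding that 48 h is an adequate washout, which the documents do not allow one to judge, nor a view on which interval the sponsor should use.

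### Does the interaction model omit the melatonin-by-genotype term, leaving the trial unable to test its title question?

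*Combined protocol and SAP*

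**What the plan says.** The Statistical methods section first sets out a mixed model "with melatonin/placebo as fixed factor, and individual as random factor". The next sentence gives a purpose and then a method. It begins "To test the interaction effect with *MTNR1B* genotype, we use the same model", and the method in full reads "we use the same model, but include genotype (carriers vs. non-carriers) as a second fixed factor". Neither this section nor the Study Protocol section writes out a product term, names the contrast to be tested, or sets a significance level for it. The rest of the Statistical methods section covers covariates, order effects and transformation of outcomes.

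The importance of the interaction is clear elsewhere. The title is "Interaction of Melatonin and MTNR1B Genotype on Glucose Control - Study 1", and the opening of the Study Protocol section lists the melatonin effect and its interaction with genotype as the two things to be determined. On design, the same section says: "Both carriers of the *MTNR1B* risk SNP and non-carriers will be randomized to the order of conditions (melatonin/placebo) in a crossover design". Treatment therefore varies within a person, and genotype varies only between people.

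**The concern.** The one change that the text makes to the base model is the addition of genotype. An analyst who entered exactly that would fit treatment plus genotype plus a random participant effect. In mixed-model software a main effect and a product term are separate entries, so the crossed term does not appear unless it is requested.

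That additive model would leave the title question unanswered. In a complete crossover a between-person term also leaves the melatonin estimate and its standard error as they were. The one new p-value would be for genotype. It asks whether carriers and non-carriers differ on average over the two conditions, and a careless reader might take it for the interaction result.

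**Working it through.** The documents give no sample size, standard deviation or effect size, so there is no figure to reproduce. The check concerns model structure and then the wording.

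**1. The two candidate models.** Let t = 1 for melatonin and 0 for placebo, and g = 1 for carriers and 0 for non-carriers.

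- Additive: mean = a + b·t + c·g. Three columns, rank 3.
- Crossed: mean = a + b·t + c·g + d·(t×g). Four columns, rank 4.

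The rank rises from 3 to 4, so the product column lies outside the span of the other three. The additive model cannot express d. This needs no assumed inputs.

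**2. A noise-free example.** Take melatonin effects of 0 in non-carriers and -1 in carriers, with equal group sizes. The additive fit gives a = 0.25, b = -0.5, c = -0.5.

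| Cell | True mean | Additive fit | Residual |
|---|---|---|---|
| Non-carrier, placebo | 0 | 0.25 | -0.25 |
| Non-carrier, melatonin | 0 | 0.25 - 0.5 = -0.25 | 0.25 |
| Carrier, placebo | 0 | 0.25 - 0.5 = -0.25 | 0.25 |
| Carrier, melatonin | -1 | 0.25 - 0.5 - 0.5 = -0.75 | -0.25 |

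The interaction contrast of the residuals is (-0.25 - 0.25) - (0.25 - (-0.25)) = -1, so the whole interaction is left in the residuals. The crossed model returns a = b = c = 0 and d = -1.

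**3. The genotype main effect is no substitute.** Assumed for illustration: 20 people per genotype group, between-person SD 1, within-person SD 0.5, two-sided alpha 0.05, no period effect, 5000 runs.

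| Melatonin effect (non-carriers, carriers) | Genotype main effect rejects | Interaction rejects |
|---|---|---|
| 0, 0 | 0.054 | 0.054 |
| -0.5, -0.5 | 0.058 | 0.045 |
| 0, -0.5 | 0.115 | 0.594 |
| +0.5, -0.5 | 0.319 | 0.992 |

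The literal additive model would therefore fail. The open question is whether the plan specifies it.

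**4. Which model the sentence specifies.** The purpose clause says an interaction is to be tested. The method clause calls genotype a second fixed factor; it does not say main effect, additive or only. Under the additive reading the sentence contradicts itself, since a model introduced to test an interaction would contain none. The added term would also do nothing for either stated aim: it leaves the melatonin estimate unchanged in complete data, and an average genotype difference is not among the aims. Under the ordinary factorial reading (two factors and their crossed term) the sentence is coherent and meets its purpose.

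**5. How much is left to the analyst.** Two treatment levels and two genotype levels give (2 - 1) × (2 - 1) = 1 degree of freedom. Before covariates or an order term, the test in complete data amounts to comparing the mean melatonin-minus-placebo difference between carriers and non-carriers. No alternative form of the contrast could be picked after seeing the data.

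**The case for a change.** The strongest case for a change is that intent does not repair a specification. This sentence is the plan's entire account of its title hypothesis, its literal method does not deliver its purpose, and writing the term out would cost one sentence and no data. If the genotype coefficient were taken for the interaction, an average carrier difference of 0.3, 0.5 or 0.8 SD of the person mean, with zero interaction, would give p < 0.05 in 15%, 34% or 69% of trials with 40 people, and in 10%, 19% or 40% with 20.

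The algebra stands, and so does the observation that no product term is written anywhere. The percentages are also computed correctly. They are the power of a two-sample t-test with noncentrality d × √(n per group / 2). For 40 people that is 0.3 × √10 = 0.95, 0.5 × √10 = 1.58 and 0.8 × √10 = 2.53; for 20 people √5 replaces √10.

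They are, however, the chance of detecting a real genotype difference, at assumed sample sizes and assumed differences. They become an error rate only if someone fits the additive model and then reports the genotype coefficient as the interaction. Nothing in the documents points to that, and the target is named as an interaction in the title, the aim and the sentence itself. An analyst who did fit the additive model would find no interaction line in the output and would see the omission at once.

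Reporting the melatonin effect with a confidence interval in each genotype group would be good practice. It corrects no rule that the plan states.

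**Conclusion.** The concern does not hold as a defect in the plan. The gap is one fixed effect with one degree of freedom, left unwritten in a sentence whose declared purpose requires it. A literal additive fit would yield no estimate of the interaction at all, but that reading sets the sentence against itself, while the crossed reading makes it coherent and leaves the analyst no discretion over the contrast. The melatonin effect itself is covered by the first model on either reading.

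This conclusion rests on reading the sentence as a whole, including its purpose clause, and on genotype being analysed in the two groups that the plan names. The structural result depends on no assumed numbers. The simulated rates and power figures rest on assumed sample sizes, differences and standard deviations; they illustrate the additive model and do not describe this trial's planned analysis.

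### Neither crossover model commits to a period (WP2 versus WP4) term, and the order test has no definition and no stated consequence

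*Combined protocol and SAP*

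**What the plan says.** The Study Protocol section describes two treatment sessions within one stay. In the first, "participants receive 5 mg of melatonin or placebo during Wake Period (WP) 2"; then "on WP4, participants receive the opposite treatment to the one received on WP2". Allocation to the two sequences is 1:1 in blocks of 2, and the section calls these sequences treatment orders: "block-randomize participants (block size 2) into two treatment orders (melatonin/placebo or placebo/melatonin". Carriers and non-carriers are both randomised to order, but the section does not say that blocks are formed within genotype.

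Statistical methods gives two models. The main one is a mixed model "with melatonin/placebo as fixed factor, and individual as random factor". For the interaction, "we use the same model, but include genotype (carriers vs. non-carriers) as a second fixed factor". Period and sequence appear in neither. The one related sentence is "We also test for any order effects". It gives no definition of order, no model or threshold for the test, and no consequence of a positive or negative result.

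**The concern.** Every participant has one session on WP2 and one on WP4. The WP4 session always follows an earlier IVGTT, a mixed meal test and more days in the laboratory, so a systematic difference between sessions is plausible whatever the treatment. A crossover analysis normally removes such a difference with a period term.

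The order sentence can be read in ways that lead to different analyses:

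- **Order means sequence.** This is how the Study Protocol section uses the word. The test then compares participant means between the two sequences. A period shift adds the same amount to every participant's mean and cancels, so this test cannot detect it.
- **Order means period, but the term is tested and not kept.** The shift stays in the error.
- **Order means period, and the term is kept when significant.** Almost no melatonin power is lost, but the model is chosen from the data.

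The first two readings give away power on both hypotheses. The interaction has a further exposure. If blocks run across genotypes, carriers and non-carriers can differ by chance in their order split, and without a period term the session shift then moves the interaction estimate in that sample.

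**Working it through.** The documents state no sample size, effect size, SD, alpha or session shift, so there is no plan figure to reproduce. What follows is an illustration on assumed inputs.

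**Set-up.** Let d be one participant's melatonin-minus-placebo difference, scaled so that its SD within sequence is 1. Let π be the WP4-minus-WP2 shift on that scale. Then d = effect + π + error for placebo/melatonin, and d = effect − π + error for melatonin/placebo. Assumptions: N = 20 and 40, half carriers, two-sided 5% tests, blocks of 2 across genotypes, 20,000 simulated trials per cell. Effects were set for a nominal 80% power with period fitted: 0.662 and 0.455 for melatonin, 1.33 and 0.91 for the interaction.

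**Standard error.** With equal sequences the ±π terms average to zero, so the melatonin estimate is unbiased (simulated bias at most 0.003). Without period, the variance of d is 1 + π², so the standard error is multiplied by √(1 + π²):

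- π = 0.25: √1.0625 = 1.03
- π = 0.5: √1.25 = 1.12
- π = 1: √2 = 1.41

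As a hand check at N = 20, the effect divided by its standard error is 0.662 × √20 = 2.96 with period fitted. Without it, at π = 1, this becomes 2.96 / 1.414 = 2.09. That equals the 5% critical value on 19 df, so power should be about one half.

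**Melatonin test** (power at N = 20 / N = 40):

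| Shift π | No period | Period kept if p<0.05 | Period always | Type I error, no period |
|---|---|---|---|---|
| 0 | 80.3 / 80.2% | 80.6 / 80.4% | 80.0 / 80.2% | about 5% |
| 0.25 | 78.3 / 78.1% | 79.9 / 79.5% | 80.0 / 79.7% | 4.2-4.4% |
| 0.5 | 72.6 / 73.1% | 79.4 / 80.0% | 80.1 / 80.1% | about 3% |
| 1 | 50.6 / 49.9% | 80.5 / 79.7% | 80.5 / 79.7% | 0.5-0.7% |

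**Can an order test give warning?** A sequence test on participant means was significant in 4.7-5.1% of trials at every shift, which is its false-positive rate. A period test was significant in 18%, 56% and 99% of trials at π = 0.25, 0.5 and 1 with N = 20, and in 33%, 87% and 100% with N = 40.

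**Interaction test** (power at N = 20 / N = 40):

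| Shift π | No period | Period kept if p<0.05 | Period always |
|---|---|---|---|
| 0 | 80.1 / 79.8% | 80.3 / 79.8% | 77.7 / 78.9% |
| 0.25 | 77.0 / 77.1% | 78.3 / 78.5% | 77.3 / 78.7% |
| 0.5 | 70.7 / 70.7% | 77.0 / 78.8% | 77.5 / 79.1% |
| 1 | 49.0 / 50.1% | 77.3 / 78.8% | 77.4 / 78.8% |

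Power with period always fitted sits a little below 80% because chance order imbalance between genotypes makes period and genotype partly overlap.

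**Interaction type I error.** Without period it averages 4.9-5.1% over randomisations, but it depends on the split that occurs. Take N = 20 with carriers split 7:3 on order and non-carriers therefore 3:7. The chance of this in either direction is 2 × C(10,7) × C(10,3) / C(20,10) = 2 × 120 × 120 / 184,756 = 16%. The interaction estimate then moves by π × (0.4 + 0.4) = 0.8π, which is 0.4 at π = 0.5. Type I error in such trials is 9.6% (200,000 simulated trials at exactly that split; smaller runs gave 8.6-9.6%), against about 5% with period fitted. At a 5:5 split it is 2.8%. If period is tested and kept only when significant, the average reaches up to 6.2% at N = 20 and π = 0.5 (repeat runs gave 5.9-6.0%).

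**Unequal sequences.** If dropout leaves unequal sequences, the melatonin estimate without period is shifted by π × (n1 − n2)/(n1 + n2): 0.1π for 11 versus 9, and 0.2π for 12 versus 8.

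**The case against.** The best defence is that the order sentence says any order effects, which can cover period as well as sequence. It follows a sentence that tests sex, age and BMI as covariates. Read together, they suggest that order factors are tested and adjusted for when significant. On that reading melatonin loses at most about 1 point of power at any shift examined. At a 1 SD shift the period test is significant in 99-100% of trials, so losing 30 points by ignoring a tested period term would mean overlooking an obvious result.

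The size is also assumed throughout. Nothing in the documents supports a shift of 0.5 to 1 SD, and one controlled stay with habitual sleep timing and a baseline day works against a large one. At 0.25 SD the melatonin loss is about 2 points. For the interaction at N = 20, always fitting period gains only 0.3 point at 0.25 SD and costs 2.4 points at zero shift. The statement that carriers of the "risk SNP and non-carriers will be randomized to the order of conditions (melatonin/placebo) in a crossover design" could mean randomisation within each genotype, in which case the chance imbalance largely disappears. Finally, the error runs in the safe direction for melatonin, and the covariate tests and transformations in the same paragraph leave model choices open too.

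Most of this limits the size and is accepted. It does not supply the missing commitment. The plan does not say that order means period or that the term is kept, and its own use of the word points to sequence. The kept-if-significant reading also carries a small cost for the interaction type I error at N = 20. That other modelling choices are open is no reason to leave this one open.

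**Conclusion.** The concern holds as a point that should be fixed. Confidence is high that the plan omits period from both models and gives the order test no definition or consequence. How much is lost depends on an unknown session shift. With no shift nothing is lost. At an assumed 0.5 SD, omitting period costs about 7 points of melatonin power and about 7 to 8 points of interaction power, and confidence intervals for the melatonin effect are 12% too wide. At 1 SD the loss is about 30 points for melatonin and 28 to 29 for the interaction.

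These figures assume 20 or 40 participants, half of them carriers, nominal 80% power, and blocks that cross genotype. There is no bias in the melatonin estimate while sequences stay balanced, and no average inflation of the interaction type I error when period is simply left out.

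**What to change.** Replace the order sentence in Statistical methods with wording such as:

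> Both mixed models include period (WP2/WP4) as a fixed effect, whatever any order test shows. Sequence (melatonin/placebo or placebo/melatonin) is reported but is not used to choose the model.

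This changes analysis-plan wording only and uses one degree of freedom. If there is no session shift, it costs under 0.5 point of melatonin power and, for the interaction, about 2 points at N = 20 or 1 point at N = 40. It needs no extra participants or procedures and no change to the randomisation.
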